11. SAFETY ANALYSES

Evaluation of safety will be performed for all patients in the SAF population.

11.1. ADVERSE EVENTS

Adverse events will be coded using MedDRA. Verbatim description of the adverse events and the MedDRA System Organ Class (SOC) and Preferred Term (PT) for all AEs will be contained in the patient data listings. A separate listing sorted by MedDRA SOC and PT will include all verbatim descriptions associated with each SOC/PT category.

Treatment emergent AEs (TEAEs) will be defined as AEs where onset occurs from the day of first dose of study medication up to and including the 2nd day following the day of last dose of study medication.

All reported AEs (whether treatment-emergent or not) will be included in by-subject AE listings. A separate listing will be created with all the distinct levels of SOC, Preferred Terms and the verbatim investigator description reported in the study. Sorting will be alphabetically by SOC, Preferred Term and then verbatim description.

If the adverse event start date is completely/partially missing, the AE will be considered a TEAE unless the following can be determined:

- The partial AE start date is sufficient to show that the AE started prior to the day of first dose of study drug.
- The AE stop date shows that the AE ended prior to the day of first dose of study drug.
- The partial AE start date is sufficient to show that the AE started after the 2 days following the day of last dose of study drug.

The incidence of TEAEs will be presented using counts and percentages of patients with AEs and tabulated by SOC and PT. SOC will be sorted alphabetically and PT within SOC will be sorted by descending frequency based on the incidence across subjects overall. If a patient has multiple occurrences (start and stop) of an event associated with a specific SOC or PT within a SOC, a patient will only be counted once in the incidence count for the SOC or PT within SOC respectively.

The following specific summary tables will be generated:

- Overall incidence of adverse events
- Incidence of TEAEs by SOC overall and by PT within each SOC
- Incidence of TEAEs related to Treatment by SOC overall and by PT within each SOC
 - If a patient reports two or more adverse events that code to the same PT, the event with the maximum relationship will be included in the table. TEAEs with a missing relationship will be assumed to be treatment related.
- Incidence of TEAEs by Maximum Severity, SOC overall and by PT within each SOC
 - If a patient reports two or more adverse events that code to the same PT, the event with the maximum severity will be included in the table. TEAEs with a missing severity will be assumed to be severe.

- Incidence of TEAEs occurring in $\geq 5\%$ of patients in at least one treatment group by SOC overall and by PT within each SOC
- Incidence of treatment-related TEAEs occurring in $\geq 5\%$ of patients in at least one treatment group by SOC overall and by PT within each SOC
- Incidence of Serious TEAEs by SOC overall and by PT within each SOC
- Incidence of TEAEs leading to treatment discontinuation by SOC overall and by PT within each SOC
- Incidence of non TEAEs following last dose of study drug for patients taking opioids by SOC overall and by PT within each SOC

Deaths, other SAEs, and AEs leading to treatment discontinuation, dose interruption, or dose reduction will be listed including the treatment group and dosing information (if applicable), start and stop dates/times of the AE, and days on study relative to the day of first dose of study drug.

The following listings will be provided:

- Listing of subjects who died
- Listing of subjects with Serious TEAEs
- Listing of subjects with non treatment-emergent SAEs
- Listing of subjects with TEAEs leading to study drug discontinuation, dose reduction, or dose interruption

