8.12 Prohibited Medications

Patients who meet the initial eligibility criteria at the Screening Visit will be asked to discontinue their current NSAID and opioid analgesic medications beginning 5 days prior to randomization (Day -5) and continuing for the duration of the study (through Day 57).

Intra-articular injections of either corticosteroids or hyaluronic acid in any joint within 3 months prior to Screening and for the duration of the study are prohibited.

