11.9.1 Adverse Events

All reported adverse events will be coded using the current version of the Medical Dictionary for Regulatory Activities (MedDRA). Verbatim descriptions of the adverse event in addition to the SOC and the preferred term (PT) will be included in the patients' data listings.

Data for AEs will be analyzed using the treatment-emergent signs and symptoms philosophy. A TEAE is defined as an AE where:

- onset occurs during exposure to study medication or within 7 days after the last dose of study medication, having been absent prior to receiving study medication, or
- onset reoccurs during exposure to study medication or within 7 days after the last dose
 of study medication, having been present but stopping prior to receiving study
 medication, or
- worsening in severity occurs during exposure to study medication relative to the pre-treatment state, when the AE is continuous.

All reported AEs (whether treatment-emergent or not) will be included in a by-patient AE listing. Only TEAEs will be included in summary tables. Adverse events that occur up to the follow-up visit will be counted as TEAEs. The incidence of TEAEs will be presented by the counts

and percentages of patients with AEs. A patient will be counted only once in the incidence count for a MedDRA PT, although a patient may have multiple occurrences (start and stop) of an event associated with a specific MedDRA PT.

Serious adverse events, AEs that lead to study drug or to study discontinuation, and AEs related to treatment will also be summarized. In addition, a table of TEAEs by severity and of TEAEs occurring in \geq 5% of the patients in at least one treatment group will be presented.

If the severity or relationship to the study drug is missing, a worst-case scenario will be assumed (i.e., it will be set to severe or definitely related relationship). All SAEs will be tabulated overall and by severity and relationship to the study drug.

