5.2.1. Adverse Events

Adverse events that occur after the signing of the informed consent up to study completion, including the Follow-up visit 7-10 days after the last dose of study medication, will be recorded on CRFs for all subjects who enter the study. An additional follow-up telephone call may be performed up to 30 days after the last dose as a final assessment of treatment-emergent adverse events unresolved at the final clinic visit attended. Information gathered by telephone related to status of adverse events will be documented in the patient case report form.

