Table 14.2.2.3.2 Change from Baseline in the WOMAC Index Stiffness Intensity Subscale Score – MMRM Analysis Full Analysis Population (FAP)

Table 14.2.2.3.3 Change from Baseline in the WOMAC Index Stiffness Intensity Subscale Score Over Time by Primary OA Joint Full Analysis Population (FAP)

Table 14.2.2.4.1 Change from Baseline in the WOMAC Index Function Intensity Subscale Score Over Time – Descriptive Statistics Full Analysis Population (FAP)

Table 14.2.2.4.2 Change from Baseline in the WOMAC Index Function Intensity Subscale Score – MMRM Analysis Full Analysis Population (FAP)

Table 14.2.2.4.3 Change from Baseline in the WOMAC Index Function Intensity Subscale Score Over Time by Primary OA Joint Full Analysis Population (FAP)

Table 14.2.3 Patient Global Impression of Change (PGIC) at Day 57/ET Full Analysis Population (FAP)

Table 14.2.4 Average Daily Use of Rescue Medication for Target Joint Pain Full Analysis Population (FAP)

Table 14.2.5 Proportion of patients withdrawing from treatment due to lack of analgesic efficacy Full Analysis Population (FAP)

Table 14.3.1.1 Overall Summary of Adverse events
Safety Population (SAF)

Table 14.3.1.2 Summary of Treatment Emergent Adverse Events (TEAEs) by System Organ Class and Preferred Term Safety Population (SAF)

Table 14.3.1.3 Summary of Treatment-Related Treatment Emergent Adverse Events (TEAEs) by System Organ Class and Preferred Term Safety Population (SAF)

Table 14.3.1.4 Summary of Treatment Emergent Adverse Events (TEAEs) by System Organ Class, Preferred Term and Maximum Severity Safety Population (SAF)

Table 14.3.1.5 Summary of Treatment Emergent Adverse Events (TEAEs) occurring in $\geq 5\%$ of patients in at least one treatment group by System Organ Class and Preferred Term Safety Population (SAF)

Table 14.3.1.6 Summary of Treatment-Related Treatment Emergent Adverse Events (TEAEs) occurring in $\geq 5\%$ of patients in at least one treatment group by System Organ Class and Preferred Term Safety Population (SAF)

Table 14.3.1.7 Summary of Serious Treatment Emergent Adverse Events (TEAEs) by System Organ Class and Preferred Term Safety Population (SAF)

Table 14.3.1.8 Summary of Treatment Emergent Adverse Events (TEAEs) leading to treatment discontinuation by System Organ Class and Preferred Term Safety Population (SAF)

Table 14.3.1.9 Summary of Non-Treatment Emergent Adverse Events (NTEAEs) Following Last Dose of Study Drug by System Organ Class and Preferred Term Safety Population (SAF)

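### SAP 11.1 limits the only SOC/PT table of late post-treatment adverse events to an undefined group of opioid users, contradicting the SAP's own Table 14.3.1.9

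*SAP*

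**What the plan says.** SAP 11.1 ends the treatment-emergent (TEAE) window early: onset must fall "up to and including the 2nd day following the day of last dose of study medication". The SOC/PT incidence tables it then lists are confined to TEAEs, with one exception: "Incidence of non TEAEs following last dose of study drug for patients taking opioids".

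The SAP table list (15.1, Table 14.3.1.9) names the corresponding output as "Summary of Non-Treatment Emergent Adverse Events (NTEAEs) Following Last Dose of Study Drug by System Organ Class and Preferred Term Safety Population (SAF", with no mention of opioids. SAP 11 states that safety will be evaluated in all Safety Population patients.

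Adverse events are collected well past day 2, "including the Follow-up visit 7-10 days after the last dose of study medication" (SAP 5.2.1). Protocol 11.9.1 uses a wider window, in which "onset occurs during exposure to study medication or within 7 days after the last dose of study medication", and adds: "Adverse events that occur up to the follow-up visit will be counted as TEAEs". It contains no opioid restriction. SAP 12 declares a single change from the protocol, to the baseline pain score. Protocol 11.1 gives the SAP precedence where the two differ.

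**The concern.** Two programmers working from SAP 11.1 and from Table 14.3.1.9 would produce different tables. The narrower reading also has no definition behind it, because neither document says which patients count as taking opioids for this display.

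At stake is the summary of the later part of the follow-up period. Visit 9 exists for a safety evaluation 7 to 10 days after the last dose. Under the 11.1 wording, a difference between CR845 and placebo in non-serious events from day 3 onward would be tabulated by SOC and PT only within the opioid group. For everyone else the reader would have by-subject listings, which give no incidence by treatment group. If the matter stays open, the population for the table could be settled after the results are known.

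**Working it through.** The point rests on comparing passages. The plan gives no figure for these events that could be reproduced.

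**1. Where an event that starts after the last dose appears**

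| Event | If SAP 11.1 is applied | If Table 14.3.1.9 is applied |
|---|---|---|
| Starts on day 1 or 2 after the last dose | TEAE tables | TEAE tables |
| Start date too incomplete to place it outside the window | TEAE tables | TEAE tables |
| Non-serious, day 3 onward, patient in the opioid group | SOC/PT table | SOC/PT table |
| Non-serious, day 3 onward, any other patient | By-subject listing; no SOC/PT table | SOC/PT table |
| Death, or serious event outside the window | Dedicated listing, no opioid limit | Dedicated listing, no opioid limit, plus SOC/PT table |

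Among non-serious events, the two readings differ only in the fourth row.

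**2. What the opioid group could be**

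- *Use at entry.* Inclusion criterion 7 admits opioid-experienced patients on a stable dose of at most 40 mg morphine equivalents. This would be a baseline characteristic.
- *Use during the study.* Protocol 8.12 has patients "discontinue their current NSAID and opioid analgesic medications beginning 5 days prior to randomization (Day -5) and continuing for the duration of the study"; the period named there ends on Day 57. Users in this period would be protocol deviators, identified after randomization.
- *Use resumed afterwards.* Protocol 9.1.4.2 has patients told at Visit 8 or early termination that they may go back to their pain medications as needed. This is also after randomization and could depend on treatment.

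The SAP does not choose among these.

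**3. How far the size can be bounded**

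Let F be the days of follow-up after the last dose (7 to 10, from SAP 5.2.1). The share of those days beyond the 2-day window is (F − 2)/F:

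- F = 7: 5/7 = 71%
- F = 10: 8/10 = 80%

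These are shares of days. They follow from the length of the TEAE window and do not measure what the opioid restriction removes. To reach events, two further quantities are needed, and the documents give neither: how onset is spread over the days, and the share f of day-3-onward events that occur in the opioid group. Assuming an even spread, the share of post-dose events in no SOC/PT table under the 11.1 wording is (F − 2)/F × (1 − f):

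| f (assumed) | F = 7 | F = 10 |
|---|---|---|
| 0.10 | 0.714 × 0.90 = 64% | 0.80 × 0.90 = 72% |
| 0.30 | 0.714 × 0.70 = 50% | 0.80 × 0.70 = 56% |
| 0.50 | 0.714 × 0.50 = 36% | 0.80 × 0.50 = 40% |

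The share exceeds one half only when f < 1 − 0.5/0.714 = 30% (F = 7) or f < 1 − 0.5/0.80 = 37.5% (F = 10). If Table 14.3.1.9 is produced as titled, it is 0% whatever f is.

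**The case against.** The strongest reply is that the intended table is probably the unrestricted one. The table list and the opening of SAP 11 both point to the whole Safety Population, and the opioid wording could be a drafting remnant. The table shells are in a separate document that was not available for this review and may settle the matter. The display is descriptive, and no test is planned on it. Serious events and deaths are protected by listings with no opioid limit. The overall adverse event summary (Table 14.3.1.1) is not worded as TEAE-only, so it may count the late events, though not by SOC and PT.

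All of that stands, and it limits the severity. It does not remove the contradiction: the body of the SAP states a restriction, and the table list omits it.

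A reader might also infer three stronger things that the documents do not support.

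- *Most post-treatment events will be missing from SOC/PT tables.* This takes the 11.1 text as the plan and ignores Table 14.3.1.9. It also needs a value of f that the documents do not give.
- *The remaining comparison rests on a post-randomization subgroup.* Use at entry is an equally open reading, so the supportable criticism is that the group is undefined.
- *The study set out to measure effects of stopping CR845.* The stated objective is the safety and tolerability of titration-to-effect administration, and effects of cessation are not named in it.

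**Conclusion.** Wrong as written, through an internal contradiction, and minor in severity. SAP 11.1 restricts the only SOC/PT summary of events after the TEAE window to an undefined opioid group. Table 14.3.1.9 and SAP 11 call for the whole Safety Population, and SAP 12 declares no such narrowing relative to Protocol 11.9.1.

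The consequence is conditional. If the 11.1 wording governs, non-serious events starting from day 3 in patients outside the group have no SOC/PT incidence by treatment group. The size cannot be computed from the documents. The percentages above depend on an assumed even spread of onset and an assumed f, and they fall to zero if the table list governs. The contradiction itself does not depend on those assumptions, nor on whether a 2-day window is a good choice.

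**What to change.** In SAP 11.1, delete the words *for patients taking opioids*. The summary then covers every Safety Population patient, as Table 14.3.1.9 is titled. Present it by treatment actually received, which is the rule for the Safety Population in SAP 7 and Protocol 11.9; randomized arm would conflict with that rule.

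If an opioid display is wanted, add it as a second table and define the group by opioid use recorded at Screening, so that membership is fixed before randomization. Prior medications are already collected from 30 days before Screening (SAP 9.6), so this needs no new data.

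While editing the section, either align the 2-day TEAE window with Protocol 11.9.1 or record it as a change in SAP 12.

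The cost is one phrase in the SAP, made before unblinding, and a check that the shell for Table 14.3.1.9 agrees. The table is already planned.

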11.2. CLINICAL LABORATORY EVALUATIONS

Chemistry and Hematology Laboratory Data

Laboratory tests from unscheduled study assessments outside planned protocol windows will not be included in the summary tables, except in the derivation of the laboratory test value at Baseline. If multiple assessments are recorded within a planned protocol window, the closest assessment to the planned time point will be used. If there are two assessments within equal proximity either side of the planned time point the earlier assessment will be used.

All laboratory tests results, whether scheduled or unscheduled, will be included in the by-subject listings. Laboratory values will be reported in standard Système International (SI) units

For all laboratory listings and summaries described in this section, the following definitions will be applied to each laboratory test:

- Screening value = the last scheduled or unscheduled (repeat) test result obtained prior to, but not including Day 1
- Baseline value = the last scheduled or unscheduled (repeat) test result obtained prior to the first dose of study drug
- End of treatment = the last scheduled test result (Day 57 or early termination) obtained within 48 hours from the last dose of study drug.

Chemistry and Hematology laboratory results at Day 57 (or early termination), and the corresponding change from baseline will be summarized for the safety population by presenting summary statistics (n, mean, SD, median, and range).

Laboratory test results will be assigned an L/N/H classification according to whether the value was below (L), within (N), or above (H) the laboratory parameter's reference range. Within each treatment arm, a 3 by 3 tables shift tables will compare the Baseline LNH classification of each laboratory test to the LNH classification at Day 57 (or early termination).

Selected laboratory test results will be flagged as markedly abnormal based on the ranges defined in Table 4 below. A summary table of the incidence of markedly abnormally low and markedly abnormally high laboratory tests results will be presented by treatment arm for all patients in the safety population. For these calculations, each subject may be counted once in the laboratory parameter value high and in the laboratory parameter low categories as applicable.

Table 4. Laboratory Ranges Used to Identify Markedly Abnormal Laboratory Values

Units		
Laboratory Parameter	Lower Limit ^a	Upper Limit ^a
Hematology		
Hemoglobin	<10 g/dL or <100 g/L	—
Platelets	<75.0 × 10 ⁹ /L or <75000/mm ³	—
Leukocytes	<3.0 × 10 ⁹ /L or <3000/mm ³	—
Leukocytes - infants, young children	<75% LLN ^b	—
Lymphocytes	<LLN	—
Lymphocytes - infants, young children	<75% LLN	—
Neutrophils	<1500 × 10 ⁶ /L or <1500/mm ³	—
Clinical Chemistry		
Electrolytes		
Potassium	< LLN	>5.5 mmol/L
Bicarbonate (CO ₂)	≤15 mEq/dL or ≤15 mmol/L	—
Liver Function Tests		
Alkaline phosphatase	—	>3 × ULN ^{b,c}
AST	—	>3 × ULN ^c
ALT	—	>3 × ULN ^c
Total bilirubin	—	>1.5 × ULN
Renal Function Tests		
Creatinine	—	>1.5 × ULN
Other Chemistry		
Calcium	<8 mg/dL or <2.0 mmol/L	>11.5 mg/dL or >2.9 mmol/L
Phosphorous	<2.5 mg/dL or <0.8 mmol/L	—
Glucose	<55 mg/dL or <3.0 mmol/L	>160 mg/dL or >8.9 mmol/L
Uric acid	—	> ULN
Cholesterol	—	>300 mg/dL or >7.75 mmol/L
Triglycerides	—	>2.5 × ULN
Albumin	<3 g/dL or <30 g/L	—

^a National Cancer Institute Common Toxicity Criteria, Version 2, Grade 2 limits (Grade 1 limit if Grade 2 limit missing).

^b LLN = lower limit of the laboratory reference (normal) range; ULN = upper limit of the laboratory reference (normal) range.

^c Modified Version 2 of the National Cancer Institute Common Toxicity Criteria.

A patient listing, sorted by patient identifier, will present all laboratory results (scheduled or unscheduled) and will include flags to identify whether a result is outside of the normal range and whether it is markedly abnormal.

A listing of all subjects with at least one markedly abnormal laboratory value will be prepared; for a given patient, this listing will not only include the laboratory results flagged as markedly abnormal, but will also present the results from all other scheduled and unscheduled evaluations of the same laboratory parameter, whether or not they are markedly abnormal.

A separate listing of patients that have liver function test results for AST or ALT > 3 ULN or total bilirubin ≥ 1.5 ULN will be presented.

Additional analyses of liver function tests (AST, ALT, and total bilirubin) will be conducted by generating shifts tables from baseline to Day 57 (or early termination) using the categories presented in Table 5 below.

Table 5. Categories for Shift Analysis of AST, ALT, and Total Bilirubin

AST/ALT	Total Bilirubin
$\leq 1 \times$ ULN	$1 \times$ ULN
$> 1 - \leq 3 \times$ ULN	$> 1 - \leq 1.5 \times$ ULN
$> 3 - \leq 5 \times$ ULN	$> 1.5 - \leq 2 \times$ ULN
$> 5 - \leq 10 \times$ ULN	$> 2 \times$ ULN
$> 10 - \leq 20 \times$ ULN	
$> 20 \times$ ULN	

Sodium Laboratory Tests

Sodium values (absolute and change from baseline as appropriate) will be summarized at each timepoint (Screening, Baseline [Day 1], Week 1 [Day 8], Week 2 [Day 15], Week 3 [Day 22], Week 4 [Day 29], Week 6 [Day 43], Week 8 [Day 57] and at Day 57 [or early termination]).

The number of patients who meet the important sodium levels (> 146 mmol/L or > 150 mmol/L) anytime between first dose and within 72 hours of final dose of study drug) will be summarized. A patient listing including all sodium test results will be programmed, flagging values that are > 146 mmol/L and > 150 mmol/L. In addition, a listing of patients with at least one sodium result > 150 mmol/L (whether during or after treatment with study drug) will be prepared; this listing will include all sodium test results for the selected patients.

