Safety and Tolerability: CR845 was well tolerated in the first 3 treatment groups (0.25- 0.5- and 1-mg tablets BID). An increase in AEs was noted in the 5-mg dose group (4 patients discontinued secondary to dizziness). In addition, although no patients were symptomatic, there was a dose-related increase in the number of slightly elevated serum sodium levels observed during the study. The majority of cases were between 146 to 147 mmol/L (normal range: 135 to 145 mmol/L). No patients exceeded a serum sodium level of 150 mmol/L.

Efficacy: All treatment groups showed a continued improvement over time in numerical rating scale (NRS) pain scores (index joint) with a percent improvement on Day 15 ranging from 25 to 31% (last observation carried forward [LOCF]) and 25 to 26% (mixed imputation).

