11.9.3 Clinical Safety Laboratory Evaluations

Mean changes from baseline to Day 57 will be presented for each of the laboratory parameters. Shift tables from baseline to Day 57 will be provided and abnormalities will be flagged (i.e., values above or below the reference ranges). The incidence of markedly abnormal laboratory results may be calculated. Additional analyses of liver function test will be completed to address the FDA guidance on the assessment of drug-induced liver injuries. Specifically, additional shift tables for AST, ALT and Total Bilirubin will be generated using the categories presented in Table 2 below.

Table 2 Categories for Shift Analysis of AST, ALT, and Total Bilirubin

AST/ALT	Total Bilirubin	
≤ 1 x ULN	1 x ULN	
> 1 - ≤ 3 x ULN	> 1 – 1.5 x ULN	
> 3 - ≤ 5 x ULN	> 1.5 – 2.0 x ULN	
> 5 - ≤ 10 x ULN	> 2.0 x ULN	
> 10 - ≤ 20 x ULN		
> 20 x ULN		

For each time point, the proportion of patients who have a serum sodium value > 146 mmol/L in each treatment group will be tabulated. In addition, a listing including all patients who had at least one serum sodium measurement post treatment > 146 mmol/L will be prepared.

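### The sodium category counts start above 146 mmol/L, so a result of 146, above the quoted normal range, is not counted, and no above-normal count is planned at Days 8 to 43

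*SAP*

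**What the plan says.** Protocol 4.2.1 describes a dose-related increase in slightly elevated sodium in the Phase 2a study. Of the elevated values it says: "The majority of cases were between 146 to 147 mmol/L (normal range: 135 to 145 mmol/L"). It adds: "No patients exceeded a serum sodium level of 150 mmol/L".

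Protocol 11.9.3 plans the count visit by visit: "For each time point, the proportion of patients who have a serum sodium value > 146 mmol/L in each treatment group will be tabulated". It also plans a listing of every patient with a post-treatment value > 146.

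SAP 11.2 plans four things for sodium:

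- descriptive statistics by visit: "Sodium values (absolute and change from baseline as appropriate) will be summarized at each timepoint";
- one count over the whole treatment period: "The number of patients who meet the important sodium levels (> 146 mmol/L or > 150 mmol/L) anytime between first dose", ending 72 hours after the final dose;
- a full listing: "A patient listing including all sodium test results will be programmed, flagging values that are > 146 mmol/L and > 150 mmol/L";
- a patient listing at the upper cut-off: "a listing of patients with at least one sodium result > 150 mmol/L (whether during or after treatment with study drug) will be prepared".

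The chemistry part of SAP 11.2 classes results as low, normal or high against the reference range and tabulates the shift from Baseline to Day 57 or early termination. SAP Section 12 says the pain-baseline definition is the only departure from the protocol.

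**The concern.** Sodium is the laboratory signal that this protocol is built around. It sets an exclusion criterion, it is measured at every clinic visit through Day 57, and it is named among the data for the Safety Monitoring Team. One would expect the sodium category table to count the kind of elevation that Phase 2a produced. Its lower cut-off instead starts one unit above the bottom of the band that the protocol itself describes, and no Phase 2a patient reached the upper cut-off. A single count over the whole period also cannot show at which visit elevations appeared, although the visits on Days 8 to 29 are where dose is decided.

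**Working it through.** No sample-size or power figure is involved. The check is of which values each rule counts, and of which planned outputs would pick up a 146.

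**Step 1. Inputs.** Normal range 135 to 145 and Phase 2a band 146 to 147 (Protocol 4.2.1); cut-off > 146 (Protocol 11.9.3, SAP 11.2); cut-off > 150 (SAP 11.2); entry excluded above 143 (exclusion criterion 13). Assumption: results are reported in whole mmol/L, which the documents do not state.

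**Step 2. Apply the rules.**

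| Result | Above 145 | > 146 | > 150 |
|---|---|---|---|
| 145 | no | no | no |
| 146 | yes | no | no |
| 147 | yes | yes | no |
| 150 | yes | yes | no |
| 151 | yes | yes | yes |

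146 is the only whole-number value above the quoted range that neither cut-off counts. It is also at least 146 − 143 = 3 mmol/L above the entry ceiling.

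**Step 3. Look for another count that would catch it.**

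- *Low/normal/high shift (SAP 11.2).* Covers Day 57 or early termination only. Sodium is in the chemistry panel (SAP 5.2.2), but Table 14.3.4.4.2 is titled for 'Other' serum chemistry and comes after separate sodium and liver-function tables, so whether sodium is included is unclear.
- *Markedly abnormal values (SAP Table 4).* No sodium row.
- *Visit summaries.* A 146 contributes to the mean, median and range, but patients above normal are not counted.
- *Listings.* A 146 is printed in the full sodium listing without a > 146 flag.

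The site sodium tests at Days 8, 15, 22, 29 and 43 therefore have no above-normal count.

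**Step 4. Size.** Let m be the share of elevated values in the 146 to 147 band and s the share of those at exactly 146. The share missed is m × s. A majority means m is roughly 0.51 to 1.00; s is not given.

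| m | s = 0 | s = 0.5 | s = 1 |
|---|---|---|---|
| 0.51 | 0% | 26% | 51% |
| 0.75 | 0% | 38% | 75% |
| 1.00 | 0% | 50% | 100% |

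The documents do not narrow the range of 0% to 100%. These are shares of values. The SAP counts patients, and loses only those whose highest result in the window is exactly 146.

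**Step 5. Protocol against SAP.**

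| Item | Protocol 11.9.3 | SAP 11.2 text | SAP table list (15.1) |
|---|---|---|---|
| Count > 146 | each time point | once, over the whole period | Table 14.3.4.2.2, layout not shown |
| Patient listing | > 146 | > 150 | Table 14.3.4.2.3, > 146 or > 150 |

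Neither difference appears in SAP Section 12. Protocol 11.1 gives the SAP precedence where the two differ, so the SAP text would govern.

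**The case against.** The best defence is that > 146 is a prespecified choice on which the two documents agree. The SAP presents it as an important level, not as the upper limit of normal. The 135 to 145 range appears in an account of a completed study, and no reference range is given for the site tests used here. Elevated values are not hidden: every result is listed, each visit has descriptive statistics, and clinically relevant laboratory findings are recorded as adverse events (Protocol 10.1.1). All of this stands. The cut-off is a weak choice, not an error or a contradiction.

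Three stronger readings are tempting and should not be drawn.

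- *A 146 is never counted or seen anywhere.* It enters the visit summaries and the full listing, and at Day 57 or early termination it may be classed high, if sodium is in the shift table and the laboratory limit is 145.
- *The trial would report far fewer elevations than occurred, or miss half of them.* That needs the split between 146 and 147, or an on-treatment mean and SD; the documents give none of these. Half of a two-integer band is not half of the patients.
- *The trial could not relate sodium to dose.* Visit-level sodium by treatment group is planned, and weekly dose is to be tabulated. Dose is chosen on tolerability and response, so a by-dose table would be confounded in any case.

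The defence does not answer two points: the missing above-normal count at Days 8 to 43, and the undeclared differences between the protocol and the SAP text. The table shells might present counts by visit, but the SAP text does not require it.

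**Conclusion.** The point holds as a gap in tabulation. With whole-number reporting and the quoted upper limit of 145, a 146 is elevated and lies in the band where most Phase 2a elevations fell, yet it enters no sodium category. No above-normal count is planned at the five visits from Day 8 to Day 43. How many patients this affects cannot be determined from the documents. If results carry decimals, the uncounted zone is everything above 145 up to and including 146.

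Separately, and without any assumption, the SAP text drops the protocol's by-visit proportion and raises the patient-listing threshold from > 146 to > 150. The latter also conflicts with the SAP's own table title. The listing as titled is not limited to > 150, so this is a matter of reconciling text, not of lost data.

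The improvement is cheap and worth making. It does not bear on efficacy.

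**What to change.** 1. In SAP 11.2 and Protocol 11.9.3, add a category above the upper limit of normal (> 145 mmol/L) beside > 146 and > 150.
2. Tabulate all three by treatment group at each time point, as the protocol already requires for > 146, and keep the whole-period count.
3. Reconcile the SAP listing text with Protocol 11.9.3 and Table 14.3.4.2.3 so that it is not limited to > 150.
4. State whether sodium is in the low/normal/high shift table, and record in SAP Section 12 any departure from the protocol that remains.

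A table by dose level at sampling is optional. It would be descriptive only, because dose is not randomized.

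The cost is some SAP and table-shell wording and a few extra rows, with no new data. The downside is that the reported incidence of sodium elevation will look higher. The change concerns tabulation only; the dosing-pause rule is not affected.
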